## 6.4 Efficacy Assessments

### Tumor Assessment

All measurable and evaluable lesions should be assessed and documented at screening and re-assessed at each subsequent tumor evaluation (see [Appendix A](#)). Assessments should include computed tomography (CT) scans with oral or IV contrast (unless contraindicated) of the chest, abdomen, and pelvis. MRI scans are allowed if CT contrast is contraindicated. Other methods of assessment should be utilized as clinically indicated.

**Tumor assessments for dose escalation cohorts, Dose Expansion Cohort C, Dose Expansion Cohort D, and Dose Expansion Cohort E** are scheduled at Screening and every 8 weeks ( $\pm$ 1 week) thereafter, ie, C3D1, C5D1, C7D1, etc. (odd-numbered cycles).

**Tumor assessments for Dose Expansion Cohort A and Dose Expansion Cohort B** are scheduled at Screening, C2D1, C3D1, C4D1, and every 8 weeks ( $\pm$ 1 week) thereafter, ie, C6D1, C8D1, C10D1, etc. (even-numbered cycles).

Subjects who permanently discontinue study drug for reasons other than progression of disease should continue to be followed for efficacy according to the schedule in [Appendix A](#).

All subjects are to have tumor assessments performed at the Treatment Completion visit, unless the subject was discontinued from treatment because of disease progression or the subject had tumor assessments performed within 14 days of the last dose of study drug.

At the investigator's discretion, CT scans may be repeated at any time if progressive disease is suspected.

Disease status will be assessed using RECIST Version 1.1 (see [Appendix C](#)). The same imaging procedure used to define measurable lesions at baseline must be used throughout the study for each patient.

At the investigator's discretion, other methods of assessment of measurable disease as per RECIST may be used. Examples of other assessment methods include tumor markers, such as prostate-specific antigen (PSA) and cancer antigen 125 (CA-125) levels for patients with prostate and ovarian cancer, respectively. However, tumor markers alone cannot be used to assess response. If markers are initially above the upper normal limit, they must normalize for a patient to be considered in complete response.

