## 8.5 Efficacy Analysis

The efficacy endpoints include PFS, ORR, DCR, and OS. Efficacy data will be listed and summarized by dose cohort and disease type.

The ORR and DCR will be summarized with percentages and 95% exact confidence intervals. The PFS rate at week 12 (Cohorts B and C) and week 16 (Cohorts D and E) and its 95% confidence intervals will be estimated by the Kaplan-Meier method. PFS, DoR, and OS will be summarized descriptively using Kaplan-Meier medians and quartiles. Percentage change in tumor size from baseline will be determined for patients with measurable disease at baseline and derived at each visit by the percentage change in the

sum of the diameters of target lesions (TLs) compared to baseline. Best percentage change in tumor size will be summarized using descriptive statistics and presented using a waterfall plot.

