### **Progression Free Survival (PFS)**

Progression free survival is defined as the time from date of first dose of study drug until the date of an objective disease progression as defined by RECIST v1.1 or death due to any cause.

Patients who have not objectively progressed or died by the date of the analysis cut-off or received any further antitumor therapy will be censored at the time of the last evaluable objective tumor assessment before the cut-off date or the antitumor therapy start date.

Progression-free survival rate is defined as the percentage of patients without evidence of progression or death at specific time points, such as week 12 (cohorts B and C), week 16 (cohort D and E) on study.

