**Appendix A Study Schedule of Events**

Date Procedure	Treatment 											Treatment Completion 	Follow-up
	Screening		Cycle 1				Cycle 2-3		Cycle 4 and onwards				
	Day -28 to Day -1	Day -7 to Day -1	Day 1	Day 8 (±1d)	Day 15 (±1d)	Day 22 (±1d)	Day 1 (±3d)	Day 15 (±3d)	Day 1 of each subsequent cycle (±3d)				
Informed consent 	X												
Tumor assessment (Dose Escalation, Expansion Cohorts C, D, E)	X		Screening, then every 8 (±1) weeks thereafter ( eg C3D1, C5D1, C7D1, etc.)								X 		
Tumor assessment (Dose Expansion Cohorts A and B only)	X		Screening, C2D1, C3D1 C4D1, and every 8 (±1) weeks thereafter (eg C6D1, C8D1, C10D1, etc.)								X 		
Medical history, demographics	X												
Concomitant medication 	X	X	X	X	X	X	X	X	X	X	X	X	
ECOG performance status		X	X		X		X	X	X	X	X	X	
Vital signs 		X	X	X	X	X	X	X	X	X	X	X	
Complete physical examination 		X											
Limited physical examination 			X	X	X	X	X	X	X	X	X	X	
Height	X												
Hematology 		X		X	X	X	X	X	X	X	X	X	

Date Procedure	Screening		Treatment 							Treatment Completion 	Follow-up
			Cycle 1				Cycle 2-3		Cycle 4 and onwards		
	Day -28 to Day -1	Day -7 to Day -1	Day 1	Day 8 (±1d)	Day 15 (±1d)	Day 22 (±1d)	Day 1 (±3d)	Day 15 (±3d)	Day 1 of each subsequent cycle (±3d)	30 (±7) days after permanent treatment discontinuation	Every 12 (±2) weeks from Treatment Completion Visit
Coagulation assay (aPTT, INR)		X		X	X	X	X	X	X	X	
Chemistry panel 		X		X	X	X	X	X	X	X	
Urinalysis 		X		X	X	X	X	X	X	X	
Echocardiogram 	X		X (Every 12 weeks ± 1 week after the first dose)							X	
Thyroid function test 	X						X		X	X	
Serum pregnancy tests 		X								X	
Urine pregnancy tests 							X		X		
Specific tumor markers  Dose Escalation, Expansion Cohorts C, D, E)	X		Screening, then every 8 (±1) weeks thereafter: C3D1, C5D1, C7D1, etc								
Specific tumor markers  Dose Expansion Cohorts A and B only)			Screening, C2D1, C3D1 C4D1, and every 8 (±1) weeks thereafter								
12-lead electrocardiogram 		X	X		X		X		X	X	
PK plasma sampling			PK samples are being collected on Days 1, 2, 14, and 15 of Cycle 1 for Expansion Cohorts B, C, D, and E. Refer to Appendix D for								

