APPENDIX 4. VISIT-WINDOW MAPPING

Document:	[REDACTED]	Version Number:	2.5
Author:	[REDACTED]	Version Date:	18Feb2022
Template No.:	[REDACTED]	Reference:	CS_WI_BS005

Effective Date: 02Dec2019

	Cycle 1				Cycle 2-3		Cycle 4 and onwards	Post-treatment
Visit	C1D1	C1D8	C1D15	C1D22	CxD1	CxD15	CxD1	
Scheduled Day [a]	1	8	15	22	1	15	1	
ECOG	Day 1		2 to EOC-3		Day -3 to 3	4 to EOC-3	Day -3 to 3	Last dose date of last cycle +8 to last dose date +37
Vital Sign	Day 1	2 to 11	12 to 18	19 to EOC-3	Day -3 to 3	4 to EOC-3	Day -3 to 3	
Hematology		1 to 11	12 to 18	19 to EOC-3	Day -3 to 3	4 to EOC-3	Day -3 to 3	
Coagulation		1 to 11	12 to 18	19 to EOC-3	Day -3 to 3	4 to EOC-3	Day -3 to 3	
Clinical Chemistry		1 to 11	12 to 18	19 to EOC-3	Day -3 to 3	4 to EOC-3	Day -3 to 3	
Urinalysis		1 to 11	12 to 18	19 to EOC-3	Day -3 to 3	4 to EOC-3	Day -3 to 3	
Thyroid function		1 to 11	12 to 18	19 to EOC-3	Day -3 to 3	4 to EOC-3	Day -3 to 3	
12-Led ECG	Day 1		2 to EOC-3		Day -3 to 3		Day -3 to 3	

[a] The scheduled day is relative to the Day 1 of each cycle.

Note: The end date of a cycle (EOC) is defined as the one day earlier than the date of Day 1 study drug administration of its next cycle. For the last cycle (where no subsequent cycle is given), the end of cycle will be defined as Day 7 relative to the last dose of the cycle.

Tumor Assessment

	Cycle 2	Cycle 3	Cycle 4	8 Weeks after D1 of Cycle 4	8 * (X + 1) Weeks after D1 of Cycle 4 [b]	Post-treatment
Visit	C2D1	C3D1	C4D1	8 Weeks after D1 of Cycle 4	8 * (X + 1) Weeks after D1 of Cycle 4 [b]	
Scheduled Day [a]	1	1	1	57	1 + 7*8 * (X + 1)	
Tumor Assessment (Cohort A and B)	-3 to (EOC-3)	-3 to (EOC-3)	-3 to (EOC-3)	End of Cycle 4 to 85	28 * (2X + 1) + 2 to 28 * (2X + 3) + 1 [d]	Last dose date of last cycle +8 to last dose date +37
	Week 8	Week 8 * (X + 1)				
Visit	Week 8	Week 8 * (X + 1) [b]				
Scheduled Day [c]	57	1 + 7*8 * (X + 1)				
Tumor Assessment (Cohort C, D, and E)	Day 2 to 85	28 * (2X + 1) + 2 to 28 * (2X + 3) + 1 [d]				

[a] The scheduled day is relative to the Day 1 for Cycle 2 to Cycle 4, but the subsequent scheduled day is relative to Day 1 of Cycle 4.

[b] X is an intergerrn starting from 1, and will take maximum value at date of last study drug administration.

[c] Scheduled day is relative to Day 1 of Cycle 1.

[d] The last windowed visit end by the last dose date.

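### Cohort C's primary week-12 PFS rate falls between its week-8 and week-16 scans, so it is shifted upward and is not like for like with Cohort B's

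*Protocol*

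**What the plan says.** Protocol 2.2.2 makes the PFS rate the primary endpoint of the expansion phase. Section 8.5 plans a Kaplan-Meier estimate of "The PFS rate at week 12 (Cohorts B and C) and week 16 (Cohorts D and E", and its PFS paragraph repeats the landmarks as "week 12 (cohorts B and C), week 16 (cohort D and E) on study". The rate is defined there as "the percentage of patients without evidence of progression or death at specific time points".

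The scan schedules differ by cohort (Protocol 6.4 and Appendix A):

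- Cohorts C, D and E: "Screening, then every 8 (±1) weeks thereafter", spelled out in 6.4 as "thereafter, ie, C3D1, C5D1, C7D1, etc. (odd-numbered cycles".
- Cohorts A and B: scans "are scheduled at Screening, C2D1, C3D1, C4D1, and every 8 weeks" after that.

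Events can also be recorded off schedule. Protocol 6.4 lets the investigator repeat CT whenever progression is suspected, and adds "All subjects are to have tumor assessments performed at the Treatment Completion visit", except after progression or a recent scan. SAP 16.1.5 dates PFS by scan and counts a progression found between visits on its actual date.

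SAP 16.2 plans Kaplan-Meier rates at 12, 16, 20 and 24 weeks without assigning a week to each cohort. SAP 5.5 states that no hypothesis is tested.

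**The concern.** Cohort C has no routine scan at its primary landmark, while Cohort B does (C4D1). A Cohort C patient who progresses between the week-8 scan and week 12 still counts as progression-free at week 12, unless the patient dies or is scanned off schedule.

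Because nothing is tested, the estimated rate and its interval are the primary result. The interval describes sampling error and does not cover a shift caused by scan timing. Protocol 1.4 describes Cohort C as a US population similar to that of the phase 3 study, so its rate is likely to be read against outside figures as well as beside Cohort B's. The plan does not say that the two week-12 rates rest on different ascertainment.

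**Working it through.** **Calendar.** Cycles last 28 days, so in elapsed days from first dose C3D1 = 56, C4D1 = 84 and C5D1 = 112. With ±7 days, Cohort C's first two routine scans fall on elapsed days 49-63 and 105-119, that is weeks 7-9 and 15-17. Week 12 is day 84, where Cohort B has C4D1.

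The visit map in SAP Appendix 4 agrees. For Cohorts C, D and E, "Scheduled day is relative to Day 1 of Cycle 1"; the Week 8 window is Day 2 to 85, and the next window (X = 1) runs from 28×3+2 = Day 86 to 28×5+1 = Day 141. The map governs by-visit summaries and not PFS dates, but it contains no week-12 tumour assessment for Cohort C.

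**The plan's own figure.** The exact 95% interval for 20/40 is 0.338 to 0.662, matching Table 16 (0.34, 0.66); the half-width is about 16 points. All six rows of Table 16 reproduce.

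**Size for Cohort C (illustration).** Assume exponential PFS with the 3.71-month median from Protocol 1.3.3: 3.71 × 30.4375 = 112.9 days and S(t) = exp(-ln2 × t/112.9). Then S(56) = 0.709, S(84) = 0.597 and S(112) = 0.503. Let f be the share of events dated exactly (deaths and off-schedule scans); the rest are dated at the next routine scan. The documents do not give f. The expected week-12 rate for Cohort C is (1-f) × S(56) + f × S(84):

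| f | Rate | Shift from 0.597 |
|---|---|---|
| 0% | 0.709 | +11.2 points |
| 20% | 0.687 | +9.0 |
| 40% | 0.664 | +6.7 |
| 50% | 0.653 | +5.6 |
| 60% | 0.642 | +4.5 |

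In 40 patients, 11.2 points is about 4.5 patients and 4.5 points about 1.8. At the phase 2 median of 4.731 months, S(56) = 0.764 and S(84) = 0.667, so the shift is +9.6 at f = 0 and +4.8 at f = 50%.

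**Cohort B and the day count.** The SAP prints no PFS formula. Its one printed duration formula in 16.2, for follow-up, adds 1. With elapsed days, an on-day C4D1 progression has PFS of 84 and counts at an 84-day landmark. With +1 it has PFS of 85 and does not count. Simulation (1,000,000 patients per scenario, 3.71-month median, no censoring before the landmark; values for f = 0 / f = 50%):

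| Day count | Scan timing | B | C | C minus B (points) |
|---|---|---|---|---|
| Elapsed | on day | 0.597 / 0.597 | 0.709 / 0.653 | 11.2 / 5.6 |
| Elapsed | uniform ±3 days | 0.649 / 0.623 | 0.709 / 0.652 | 6.1 / 2.9 |
| Elapsed | uniform ±7 days | 0.657 / 0.626 | 0.709 / 0.653 | 5.3 / 2.7 |
| +1 | on day | 0.709 / 0.655 | 0.709 / 0.655 | 0 / 0 |
| +1 | uniform ±3 days | 0.664 / 0.632 | 0.709 / 0.655 | 4.5 / 2.3 |
| +1 | uniform ±7 days | 0.665 / 0.633 | 0.709 / 0.655 | 4.5 / 2.3 |

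Differences are taken before rounding. The same one-day question affects Cohorts D and E: an on-day C5D1 progression has PFS of 112 or 113 against a 112-day landmark.

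**Window-close reads.** These count every landmark scan made within its window. Unscheduled detection aside, the expected rate is the target; exactly dated events after the landmark pull it down slightly.

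- Cohort C, week 16 read at day 119: S(119) = 0.482, so at f = 50% the rate is (0.503 + 0.482)/2 = 0.492, about 1 point under the target of 0.503. Read at day 112 with scans spread over ±7 days, it would be 0.554 to 0.606.
- Cohort B, week 12 read at day 87: S(87) = 0.586, giving (0.597 + 0.586)/2 = 0.592 at f = 50%, about half a point low.

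**The case against.** Several points on the other side stand.

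- No B-versus-C comparison is planned. The cohorts differ by design in prior TAS-102 or regorafenib, so a difference between them would be confounded whatever the scan schedule.
- Both schedules are printed, and the rate is defined by evidence of progression, so Cohort C's figure is a valid estimate of what the protocol defines. A reader might infer that it is wrong or cannot be estimated; the documents do not support that.
- A reader might infer a fixed B-C gap of several points, with Cohort B unaffected. That needs an elapsed-day count the documents never state. With +1 and on-day scans, Cohort B also carries only its week-8 result and the gap vanishes.
- The quoted medians may themselves be scan-dated: 3.71 months is 112.9 days and 1.84 months is 56.0 days, close to weeks 16 and 8. Treating 3.71 months as a latent median is an assumption.
- The +11 end requires no deaths or off-schedule scans before week 12, and even that is below ±16 points.

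These limit the size and the comparison. They do not remove the upward shift in Cohort C's own estimate, which does not shrink with sample size.

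**Conclusion.** The point holds for Cohort C's own primary estimate. The scan calendar is certain; the size is not. Under exponential PFS with a 3.71-month median the shift is about +4.5 to +11 points for 60% down to 0% of events dated exactly.

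The B-C gap from scheduling alone lies anywhere from about 0 to 11 points, depending on the unstated day count, actual scan timing and f. The main effect is therefore on each cohort's own rate and on reading it against outside rates. No size is given for Cohorts D and E, because the documents quote no breast cancer median; their shift is zero if on-day scans count at the landmark, and otherwise upward. Severity is minor to moderate.

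**What to change.** Amend SAP 16.2, with a dated note in SAP 2.4 stating whether any cohort's data had already been analysed, since SAP 3 allows early looks:

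1. State one PFS day count and landmark day so that an on-day landmark scan counts at its landmark, for example elapsed days from first dose with week 12 = 84 and week 16 = 112.
2. Keep Cohort C's week-12 rate as the protocol-named figure. Footnote that it reflects the week-8 scan plus deaths and off-schedule scans and is not like for like with Cohort B's. Report beside it the already planned week-16 rate, read at elapsed day 119 when the C5D1 window closes, as the scan-supported estimate.
3. As a sensitivity analysis, read Cohort B at elapsed day 87, the close of the ±3-day visit window in Protocol 6.2 and Appendix A (day 91 only if ±7 days is taken to apply to C4D1), and Cohorts D and E at elapsed day 119.

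As a minor alignment, SAP 2.3.2 should name the PFS rate rather than PFS and carry over the protocol's week for each cohort.

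The cost is a footnote and a few table rows, with no extra scans. The added figures may be lower: in the illustration Cohort C would show about 0.49-0.50 at week 16 beside 0.65-0.71 at week 12 (f from 0 to 50%), partly because week 16 is later. Window-close reads also carry a downward shift of up to about 1 point at f = 50%.

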### **Objective Response Rate (ORR)**

The ORR is defined as the percentage of patients with at least one best overall response (BOR) of CR or PR according to RECIST Version 1.1. To be assigned a status of PR or CR, changes in tumor measurements must be confirmed by repeat assessments performed no less than 4 weeks after the criteria for response are first met.

The BOR in an individual patient according to the RECIST criteria is the best response recorded from the start of treatment until documented RECIST progression or the date of any further anticancer therapy, whichever comes first. In the case of a patients without documented progression or additional anticancer therapy, BOR is determined using all available visit up until the last evaluable visit response.

### **Disease Control Rate (DCR)**

Disease control rate is defined as the percentage of patients with a best overall response of CR, PR, or SD.

### **Progression Free Survival (PFS)**

Progression free survival is defined as the time from date of first dose of study drug until the date of an objective disease progression as defined by RECIST v1.1 or death due to any cause.

Patients who have not objectively progressed or died by the date of the analysis cut-off or received any further antitumor therapy will be censored at the time of the last evaluable objective tumor assessment before the cut-off date or the antitumor therapy start date.

Progression-free survival rate is defined as the percentage of patients without evidence of progression or death at specific time points, such as week 12 (cohorts B and C), week 16 (cohort D and E) on study.

### **Duration of Response (DoR)**

Duration of response is defined as the time from date of the first objective response, CR or PR, whichever comes first, until the occurrence of documented disease progression or death in the absence of disease progression. If a patient does not progress following a response, then the DoR will be censored at the same time of PFS.

### **Percentage Change in Tumor Size from Baseline**

Percentage change in tumor size will be determined for patients with measurable disease at baseline and is derived at each visit by the percentage change in the sum of the diameters of target lesions compared to baseline.

### **Overall Survival (OS)**

Overall survival is defined as the time from the date of the first dose of study drug until the date of death (any cause). Patients who did not die at the time of the statistical analysis will be censored at the time at which they were last known to be alive.

## **8.6 Determination of Sample Size**

The total number of patients enrolled will depend on the number of dose escalations and the need to further characterize individual cohorts of single-agent fruquintinib administered at the RP2D.

### **Dose Escalation Phase**

The sample size may vary depending on the number of dose levels evaluated and the number of DLTs observed in each cohort. Patients who are considered not evaluable for DLT or PK will be replaced. The sample size may increase when these patients are replaced.

### **Dose Expansion Phase**

The primary objective of the dose expansion phase is to evaluate the anticancer activity of fruquintinib in patients with advanced solid tumors, treated at the RP2D from the dose escalation phase.

Approximately 6 patients with advanced, refractory solid tumors of any type will be enrolled in Cohort A. This sample size is not based on a formal statistical assumption.

Additionally, enrollment in disease specific cohorts is planned as follows:

- 40 patients in Cohort B (refractory mCRC with progression on TAS-102 and/or regorafenib)
- 40 patients in Cohort C (refractory mCRC that has progressed on standard chemotherapies and relevant biologics but has NOT received TAS-102 or regorafenib)
- 15 patients in Cohort D (HR+/Her2- mBC)
- 15 patients in Cohort E [triple negative breast cancer (TNBC)]

The number of patients in each cohort can provide adequate precision for the estimated incidence rates of patients having a specific AE, patients with CR/PR (ORR), patients with

CR/PR/SD (DCR), or PFS rate at a specific time point.

Shown below in [Table 15](#) and [Table 16](#) are the range of incidence rates and the corresponding 95% Confidence Intervals (CI) for a sample size of 15 and 40 patients, respectively. As shown in the table, the 95% CI is approximately equal to an estimated incidence rate of  $\pm 16\%$  to 28% for a sample size of 15 patients and estimated incidence rate of  $\pm 7\%$  to 16% for a sample size of 40 patients.

**Table 15 Estimated Incidence Rates and 2-Sided 95% Confidence Intervals for N=15 Patients**

Number of Cases	Observed Incidence Rate	95% CI Lower Limit	95% CI Upper Limit
0	0	0.00	0.22
3	0.2	0.04	0.48
6	0.4	0.16	0.68
9	0.6	0.32	0.84
12	0.8	0.52	0.96
15	1	0.78	1.00

95% Clopper-Pearson Interval for binomial distribution

**Table 16 Estimated Incidence Rates and 2-Sided 95% Confidence Intervals for N=40 Patients**

Number of Cases	Observed Incidence Rate	95% CI Lower Limit	95% CI Upper Limit
0	0	0.00	0.09
4	0.1	0.03	0.24
10	0.25	0.13	0.41
20	0.5	0.34	0.66
30	0.75	0.59	0.87
40	1	0.91	1.00

95% Clopper-Pearson Interval for binomial distribution

## **9 ETHICS**

### **9.1 Independent Ethics Committee/Institutional Review Board (IEC/IRB)**

This protocol, protocol amendment(s), the ICFs, any information to be given to the patient, and relevant supporting information must be submitted by the PI to the IEC/IRB for review and approval before the study is initiated. In addition, any patient recruitment materials must be approved by the IEC/IRB.

The PI is responsible for providing written summaries of the status of the study to the Independent Ethics Committee/Institutional Review Board (IEC/IRB) annually or more frequently in accordance with the regulatory requirements and policies and procedures established by the IEC/IRB. Investigators are also responsible for promptly informing the IEC/IRB of any protocol changes or amendments and of any unanticipated problems involving risk to human patients or others.

In addition to the requirements to report protocol-defined AEs to the sponsor or its designee, investigators are required to report promptly to their respective IEC/IRB all unanticipated problems involving risk to human patients. Some IECs/IRBs may want prompt notification of all SAEs, whereas others require notification only about events that are serious, considered related to study drug, and unexpected.

### **9.2 Ethical Conduct of the Study**

The study will be conducted in accordance with the protocol, International Conference on Harmonization (ICH) guidelines, applicable regulations and guidelines governing clinical study conduct and the ethical principles that have their origin in the Declaration of Helsinki.

### **9.3 Patient Informed Consent**

The investigator or his/her representative will explain the nature of the study to the patient and answer all questions regarding this study. Before any study-related screening procedures are performed on the patient, the ICF will be reviewed, signed, and dated by the patient and the person who administered the informed consent. A copy of the signed informed consent document will be given to the patient and the original will be placed in the patient's medical record and must be available for verification by study monitors at any time. If applicable, the ICF will be provided in a certified translation of the local language.

The ICF should be revised whenever there are changes to procedures outlined in the document or when new information becomes available that may affect the willingness of the patient to participate.

For any updated or revised ICFs, the case history for each patient shall document the informed consent process and that written informed consent was obtained from the patient for the updated/revised ICF for his/her continued participation in the study. The final revised IEC/IRB-approved ICF must be provided to Hutchison MediPharma for regulatory purposes.

Signed and dated ICFs must remain in each patient's study file and must be available for verification by study monitors at any time.

